127   12.6% of patients with diagnosed diabetes (18.8 millions)   136

128   have an HbA1c >9%. In the Emory Health Care system   137

129   the largest academic health system in Georgia, over   138

130   64,000 patients have a diagnosis of diabetes, with ~16%   139

131   having an HbA1c>9% (Figure 1). The evidence on the   140

132   management of patients with T2D and very high HbA1c   141

133   very limited, with most studies excluding patients with   142

134   HbA1c > 10%. Figure 1. HbA1c Distribution in Patients   143

135   144

[figure not shown]
136   145

137   146

138   147

139   148

140   149

150       In a recent multi-national study of insulin-naïve patients with T2D, treated with or without  
151   oral agents, showed that only ~40% of patients with HbA1c > 9% were started on basal insulin.  
152   Moreover, the study showed that only 20.9% of such patients achieved HgA1c target (< 7%) at 3  
153   months after initiating basal insulin, indicating a need for coverage of prandial-related  
154   hyperglycemic excursions. Notably, failure to achieve HbA1c targets at 3 months was associated  
155   with an increased risk of not achieving HbA1c targets at 24 months, with < 30% of patients  
156   achieving glycemic targets. This study suggests that providers delayed initiation of basal insulin  
157   as recommended by national guidelines, and frequently failed to intensify therapy to cover  
158   prandial-related hyperglycemic excursions. A recent study in ambulatory patients with T2D and  
159   high HbA1c (>10%) on metformin and sulfonylurea treatment, randomized patients to  
160   combination (COMB) therapy with exenatide plus pioglitazone vs basal-bolus insulin regimen.  
161   COMB provided greater HbA1c reduction at 6 months, with significantly less weight gain.  
162   However, the rates of hypoglycemia were unusually high, up to 56% and 83% in COMB and BB,  
163   respectively. Our group recently validated the efficacy of a hospital discharge algorithm based  
164   on the admission HbA1c. Among those patients with high admission HbA1c> 9% (n: 81), 54  
165   were discharged on basal-bolus insulin regimen. Mean admission HbA1c of 11.1% decreased to  
166   8.8% and to 8.0% after 4 and 12 weeks of hospital discharge (p<0.01), respectively. However, up  
167   to 44% of patients had hypoglycemia (BG < 70 mg/dl) during follow-up. Thus, there is a critical  

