218 hyperglycemia. GLP1-RAs decrease post-prandial glycemic excursions and complement  
219 basal-insulin therapy by enhancing endogenous insulin responses in a glucose-dependent  
220 manner, inhibiting glucagon secretion, slowing gastric emptying and promoting satiety. This  
221 combination has been shown to provide better glycemic control, less hypoglycemia, less weight  
222 gain, and reduce glycemic variability compared to basal bolus therapy or GLP1-RA  
223 alone. IDegLira is a novel fixed-ratio combination of degludec 100 u/ml and liraglutide  
224 3.6 mg in a pre-filled pen. IDegLira has been shown to improve glycemic control, with lower risk  
225 of hypoglycemia, less weight gain, and better patient satisfaction compared to basal-bolus or  
226 stepped-up basal therapy. Pharmacokinetics studies showed that IDegLira provided  
227 coverage over the 24-hours interval at steady levels. In the recent DUAL V trial, IDegLira  
228 resulted in greater HbA1c reduction, weight loss and less hypoglycaemia, compared to up-  
229 titration of insulin glargine in patients with T2D with HbA1c 7-10%. More recently in the DUAL  
230 VII trial, patients with HgA1c 7-10% randomize to IDegLira had similar HbA1c reduction, but  
231 with an 89% reduction in the rate of severe or confirmed symptomatic hypoglycemia and weight  
232 loss compared to basal-bolus insulin. Thus, IDegLira is an attractive and option for patients  
233 with severe hyperglycemia, due to potent HbA1c reduction, lower hypoglycemic risk, and  
234 flexibility of once-daily administration, compared to up to five injections per day in basal-bolus  
235 regimen. However, no previous studies have compared the efficacy and safety of IDegLira in  
236 patients with high HbA1c >9-15%.

237

238

239 **SIGNIFICANCE AND INNOVATION:**

240                   The proposed study will test three innovative questions in patients with poorly controlled  
241                   T2D and HbA1c  $\geq 9\%$ : 1) whether IDegLira, a novel FRC of degludec and liraglutide, results in  
242                   similar glycemic control, 2) less hypoglycemia, less glycemic variability and less weight gain  
243                   compared to a basal-bolus, and 3) whether IDegLira results in better patient satisfaction and  

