271                   (responder’s rate)
- 272                   • Percent of patients reaching A1c  $< 7.5\%$  without weight gain and no hypoglycemia”
- 273                   • Percent of patients with A1c  $> 10\%$  and  $> 11\%$  that achieve A1c  $< 7.5\%$  and  $< 8\%$

- Percent of patients with HbA1c <7.0% at 26 weeks and no weight gain
- Percent of patients with HbA1c <7.0% at 12 weeks and no hypoglycemia
- Incidence of documented symptomatic hypoglycaemia, defined as an event with typical symptoms of hypoglycaemia accompanied by SMBG or CGM (<70 mg/dL and < 54 mg/dL) that occurs at any time of the day
- Incidence of asymptomatic hypoglycaemia, defined as no typical symptoms reported by the subject but detected by SMBG or CGM (<70 mg/dL and < 54 mg/dL)
- Incidence of severe hypoglycaemia, defined as severe cognitive impairment requiring assistance from another person
- Incidence of nocturnal symptomatic hypoglycaemia, defined as an event with typical symptoms of hypoglycaemia accompanied by SMBG or CGM <70 mg/dL and < 54 mg/dL that occurs between 00:00 and 05:59 hrs
- Incidence of nocturnal asymptomatic hypoglycaemia, defined as SMBG or CGM <70 mg/dL and < 54 mg/dl between 00:00 and 05:59 hrs
- Percentage of time below 70 mg/dL and <54 mg/dl as obtained by CGM
- Percentage of time in range (BG 70-180) as measured by CGM
- Glycemic variability, as measured by SD (standard deviation), %CV (coefficient of variance), Mean Amplitude Glucose Excursions (MAGE)
- Patient satisfaction and quality of life, as measured by the DTSQ and T R I M - D questionnaires
- Number of emergency room visits and hospital readmissions
- Change from baseline in total insulin dose (units/day)
- Number of treatment emergent AE

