**Assessments for Safety**

801 The safety endpoint of the study will be incidence of hypoglycaemia, as measured by the

802 current standard-of-care of POC monitoring. Subjects will complete an 8-point POC BG log  
803 before weeks -1, 12, 26. In addition, we will perform blinded/professional CGM studies for 7  
804 days, during week -1, 12, and 26. CGM will allow better detection of hypoglycemic events,  
805 particularly asymptomatic and nocturnal hypoglycemia, usually not detected by POC monitoring.  
806 It will also provide critical information on time in glycemic range and glycemic variability. We will  
807 also compare differences in glycemic variability, by SD, %CV and MAGE. GV will be calculated  
808 by mean daily standard deviation (SD) of glucose values in absolute terms, and as a percentage  
809 of variance from the overall mean (%CV). These are measures of dispersion of glucose values  
810 around a measure of central tendency, which represents the overall glucose excursion during  
811 the study. We will also analyze GV by mean amplitude of glycemic excursion (MAGE), which  
812 represents the average of all BG excursions (up or down), with a magnitude of > 1 standard  
813 deviation of all BG measures.

814

815 **Potential Risks to the Subjects:**

816 **Hypoglycemia.** It is possible that following the proposed protocol, subjects receiving IDegLira  
817 or Basal-bolus may develop hypoglycemia, as defined above.

818 **Gastrointestinal side effects**, including nausea and vomiting are more common in patients  
819 treated with liraglutide compared to placebo. The frequency of nausea and vomiting is reported  
820 in up to 5-15% patients receiving IDegLira. The number of adverse events will be collected at  
821 each telephone contact or clinic visit. There have been few reported events of acute  
822 pancreatitis. Subjects should be informed of the characteristic symptoms of acute pancreatitis:  
823 persistent, severe abdominal pain. If pancreatitis is suspected, Degludec-liraglutide should be  
824 discontinued. If the investigator suspects acute pancreatitis, all suspected drugs should be  
825 discontinued until confirmatory test have been conducted and appropriate treatment should be  
826 initiated. Subjects diagnosed with acute pancreatitis (as a minimum 2 of 3: characteristic  
827 abdominal pain, amylase and/or lipase >3xUNR or characteristic findings on CT scan/ MRI  

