1042 An AE is any undesirable medical event occurring to a subject in a clinical trial, whether  
1043 or not related to the trial product(s). This includes events reported from the first trial related  
1044 activity after the subject has signed the informed consent and until post treatment follow-up  
1045 period as defined in the protocol.

1046 **Adverse Reaction (AR)**

1047 An AR is an adverse event for which the causal relationship between the product and the  
1048 adverse event is suspected.

1049 The following should not be recorded as AEs, if recorded as medical history/concomitant illness  
1050 on the CRF at screening:

- 1051 • Pre-planned procedure, unless the condition for which the procedure was planned has  
1052 worsened from the first trial related activity after the subject has signed the informed consent
- 1053 • Pre-existing conditions found as a result of screening procedures

1054  
1055  
1056 **Clinical Laboratory Adverse Event:**

1057 A clinical laboratory AE is any clinical laboratory abnormality regarded as clinically  
1058 significant i.e. an abnormality that suggests a disease and/or organ toxicity and is of a severity,  
1059 which requires active management, (i.e. change of dose, discontinuation of trial product, more  
1060 frequent follow-up or diagnostic investigation).

1061

1062 **Serious Adverse Event (SAE):**

1063 A serious AE is an experience that at any dose results in any of the following:

- 1064 • Death
- 1065 • A life-threatening\* experience
- 1066 • In-patient hospitalization or prolongation of existing hospitalization
- 1067 • A persistent or significant disability/incapacity
- 1068 • A congenital anomaly/birth defect
- 1069 • Important medical events that may not result in death, be life-threatening\*, or require  
1070 hospitalization may be considered an SAE when, based upon appropriate medical judgement,  
1071 they may jeopardize the subject and may require medical or surgical intervention to prevent one  
1072 of the outcomes listed in this definition
- 1073 • Suspicion of transmission of infectious agents

1074 \*The term life-threatening in the definition of SAE refers to an event in which the subject was at  
1075 risk of death at the time of the event. It does not refer to an event which hypothetically might  
1076 have caused death if it was more severe.

1077

1078 **Serious Adverse Drug Reaction (SADR):**

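### No between-arm comparison is pre-specified for the gastrointestinal, gallbladder or pancreatic harms the protocol attributes to IDegLira or liraglutide, and the pooled adverse-event count does not say whether hypoglycaemia is included

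*Combined protocol and SAP*

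**What the plan says.** Under ENDPOINTS, the last secondary outcome is "Number of treatment emergent AE". It gives no event type, seriousness or per-patient incidence, and treatment emergent is not defined. The same list has "Number of emergency room visits and hospital readmissions" and ten items that involve hypoglycaemia, four of them HbA1c composites. Three composites include absence of weight gain.

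Assessments for Safety states: "The safety endpoint of the study will be incidence of hypoglycaemia, as measured by the" current standard of point-of-care monitoring. Directly below, Potential Risks to the Subjects sets out harms of the test drug. "The frequency of nausea and vomiting is reported" "in up to 5-15% patients receiving IDegLira". It adds that a few cases of acute pancreatitis have been reported, and cites gallbladder events in 3.1% on liraglutide v 1.9% on placebo from a cardiovascular outcomes trial.

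Statistical Methods mentions adverse effects once, as an example of a secondary measurement, and names no categories. Interim Analysis compares deaths between groups at a two-sided alpha below 0.01. The Medical Events of Special Interest are medication error and transmission of an infectious agent.

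The definition reads "An AE is any undesirable medical event occurring to a subject in a clinical trial, whether" or not it is related to the trial product. Hypoglycaemia is not excluded. Yet Table 1 has separate rows for adverse events and hypoglycaemia, and Visit Procedures, Telephone Visits, Follow-up Visits and Visit 12 name them as separate items.

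**The concern.** The two regimens are expected to have opposite harms: gastrointestinal events on IDegLira and hypoglycaemia on basal-bolus. A single total nets one against the other if both are counted. Hypoglycaemia would then also appear twice, once in its own endpoints and again in the total.

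The plan compares the expected advantage of IDegLira on many measures. It pre-specifies no contrast for the disadvantage that it describes itself. The protocol suggests the regimen could become standard of care for this population, and a reader weighing that would want both sides compared with equal care. The trial is also open-label, so a counting rule left open now could be settled after the data by arm are known.

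**Working it through.** **The plan's own figure.** No power or sample size is given for any adverse-event outcome. The only such figure is 57 per group for HbA1c, and it reproduces. The normal approximation is n = 2(1.645 + 0.842)² × 0.85² / 0.4² = 55.8, so 56. The exact t calculation gives 79.7% power at 56 and 80.3% at 57. Attrition gives 57/0.80 = 71.25, so 72, and the plan recruits 75. The illustration below uses 75 per arm.

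**Inputs from the documents.**
- Gastrointestinal events on IDegLira: 15%, the top of the stated 5-15%.
- Hypoglycaemia on basal-bolus: 44%. The background reports that up "to 44% of patients had hypoglycemia (BG < 70 mg/dl) during follow-up", in patients with HbA1c above 9%.
- Reduction on IDegLira: 89%. The background cites a trial against basal-bolus "with an 89% reduction in the rate of severe or confirmed symptomatic hypoglycemia and weight" loss.

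**Assumptions not in the documents.**
- Gastrointestinal events on basal-bolus: 2% (varied below).
- The 89% event-rate reduction is applied to incidence.
- One event per affected patient and no other adverse events.

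**Expected totals per 75 patients.**

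| Component | IDegLira | Basal-bolus |
|---|---|---|
| Gastrointestinal | 75 × 0.15 = 11.25 | 75 × 0.02 = 1.5 |
| Hypoglycaemia | 75 × 0.44 × 0.11 = 3.63 | 75 × 0.44 = 33 |
| Total with hypoglycaemia | 14.9 | 34.5 |
| Total without hypoglycaemia | 11.25 | 1.5 |

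The direction reverses with the counting rule.

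**Sensitivity to the hypoglycaemia reduction.** With a 50% reduction the totals are 11.25 + 16.5 = 27.75 v 34.5, and in 20,000 simulated trials the total is lower on IDegLira in about 83%. The totals are equal when 33(1 − r) + 11.25 = 34.5, so r = 1 − 23.25/33 = 0.295, a reduction of about 30%.

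**What a direct gastrointestinal comparison could show (75 per arm, Fisher's exact test, two-sided 0.05).**
- 15% on IDegLira: power is about 98%, 78%, 67% and 44% if basal-bolus is 0%, 2%, 3% and 5%.
- 5% on IDegLira: power is about 17% down to 3% if basal-bolus is 0% to 3%.
- At 15% v 2%, the risk difference is 13 points. Its standard error is √(0.15 × 0.85/75 + 0.02 × 0.98/75) = 0.044, so the 95% CI is about 4 to 22 points.

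**Gallbladder.** 75 × 0.031 = 2.3 v 75 × 0.019 = 1.4 patients, with power about 7%. No rate is given for pancreatitis.

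**The case against.** The strongest reply is that the documents repeatedly treat hypoglycaemia and adverse events as separate data. If that separation carries into the analysis, hypoglycaemia hides nothing and, on the same inputs, the total is higher on IDegLira (about 11 v 1.5). This stands as far as it goes: masking is conditional. But the definition would admit hypoglycaemia and no sentence settles the matter. Even with hypoglycaemia out, the single count pre-specifies no gastrointestinal, gallbladder or pancreatic contrast.

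Second, a reader might infer that known harms will go unreported. The documents do not support that. Adverse events are collected at nearly every contact, diagnosis is a minimum recorded item, and nothing prevents tabulation by type. The protocol says most of the cited gallbladder events required hospitalisation or cholecystectomy, so some may surface among readmissions. What is missing is the pre-specified comparison.

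Third, the size of the illustration depends on generous inputs. The 89% comes from patients with HbA1c 7-10% and covers severe or confirmed symptomatic events, whereas the 44% is any glucose below 70 mg/dl. The 44% also comes from a group of 81 in which 54 were on basal-bolus. Other adverse events would dilute the contrast. In simulation (difference in totals divided by the square root of their sum), the total including hypoglycaemia is nominally significantly lower on IDegLira in about 85% of trials with no other events. That falls to about 42% or 28% if each patient in both arms has on average 0.5 or 1 other event. With a 50% hypoglycaemia reduction and no other events it is about 9%. This objection stands against any claim that the total would reliably produce a significant result. It does not affect the point that its direction depends on an unstated rule.

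**Conclusion.** The point holds as a gap in pre-specification. The plan names specific harms of the test drug, compares none of them between arms, and covers them only through a pooled count whose contents are not settled.

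The figures of about 15 v 34 and about 11 v 1.5 are illustrative. They rest on the assumed 2% gastrointestinal rate on basal-bolus, the top of the stated range on IDegLira, the transferred 89% reduction, one event per affected patient and no other adverse events. They show that the endpoint can change direction, not what the trial will find.

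Two stronger readings go too far. That hypoglycaemia swamps the other harms is true only if it is counted. That the pooled total is the sole comparison of harms beyond hypoglycaemia and acute care overlooks the interim comparison of deaths and the weight-gain composites. The primary HbA1c analysis is unaffected. This is an inexpensive improvement worth making before the data are compared by arm.

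**What to change.** Replace the pooled item with three:

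- (a) the number and percent of patients with at least one treatment-emergent adverse event, and event counts, excluding hypoglycaemic episodes, which are reported under their own endpoints;
- (b) the percent of patients with at least one gastrointestinal adverse event (nausea, vomiting, diarrhoea), compared between arms with a risk difference and 95% CI;
- (c) descriptive counts by arm of gallbladder events, pancreatitis, and adverse events leading to discontinuation of study drug.

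Define treatment emergent in the same place. The adverse-event records already being collected should supply all of this, with no new visits and no change to treatment.

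The cost is one revised endpoint line and a few tables, and possibly a less favourable adverse-event picture for IDegLira. At this sample size gallbladder and pancreatitis counts can only be descriptive. If the IDegLira gastrointestinal rate is near 5%, item (b) has little power, and the interval should be read as the result rather than the p-value.

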## 300 **STUDY DESIGN AND METHODS:**

301 The study is a 26-week, open-label, treat-to-target, two-arm parallel, randomized, controlled trial  
302 investigating the efficacy and safety of IDegLira versus basal-bolus insulin in patients with T2D.  
303 Patients with HbA1c  $\geq$  9% treated with oral antidiabetic agents and/or basal insulin therapy  
304 (TDD  $\leq$  50 units) will be randomized in a 1:1 manner to receive IDegLira or basal-bolus insulin  
305 regimen (plus metformin unless contraindicated), as shown in Fig 2. Subjects will have contact  
306 with the study team via clinic visits or phone contacts for a total of 29-weeks, as shown in the  
307 figure below (Fig 2 and Table 1).

308  
309 Figure 2. Study design

311 Legend: OAD: Oral anti-diabetic agents, EOT: End-of-treatment, FUP: Follow-up safety visit

312  
313 Visits will be distributed as follows: initial screening visit/CGM insertion (visit 1), 2 weeks of  
314 screening/run-in period, randomization visit (visit 2), 26-week treatment period (visits 4-18), and  
315 a follow-up safety visit after the end the 26-weeks treatment period (visit 19). Subjects will have  
316 contact with the study team via clinic visits or phone contacts for a total of 9 clinic visits and 9  
317 telephone contacts. This study will include patients with a known history of T2D, age 18-80,  
318 treated with oral antidiabetic agents including metformin, sulfonylurea, repaglinide/nateglinide,  
319 pioglitazone, DPP4 inhibitors, SGLT2 inhibitors, (monotherapy + basal insulin) or in combination  
320 therapy (2-3 agents), and/or on basal insulin at a total daily dose (TDD) of  $\leq 50$  units.

321 Participants previously using basal insulin [neutral protamine hagedorn (NPH), mixed insulin,  
322 detemir or glargine insulin], will be switched to study-provided Degludec or IDegLira and/or  
323 Aspart pens. Metformin will be continued at same dose during the study, unless contraindicated.  
324 Patients previously treated ambulatory with basal-bolus insulin therapy and/or GLP1-RA will be  
325 excluded. Patients transiently treated with basal-bolus insulin (standard-of-care treatment)  
326 during hospital admission can be included. Recommendations on insulin adjustment will be  
327 provided at each visit or phone encounter by a study physician.

### 328 329 **Rationale for study design**

330 Based on the DUAL trial program, a total of 26 weeks of treatment is sufficient to reach  
331 stable HbA1c levels, with a minimum of 12 weeks in the maintenance period. This timeline has  
332 been previously shown to be sufficient to collect data for efficacy and safety. A parallel design  
333 will allow for assessment of efficacy and safety in the shortest time in each group, compared to  
334 a cross-over design. An open label design allows us to use a simpler regimen with a single  
335 injection of IDegLira, as blinding the subjects will require a double dummy design with three  
336 extra subcutaneous injections per day, thus imposing a high burden on subjects, thereby  
337 increasing the non-compliance and withdrawal rates. Patients in both arms will  
338 receive the same degree of self-monitoring and follow-up. Patients will have

339 blinded CGM to avoid the bias of glycemic improvement by using real-time glucose  
340 data from CGM. The primary endpoint will use HgA1c changes, a standard  
341 laboratory test shown to correlate with risk of diabetes complication, thus limiting  
342 the assessment bias. Secondary endpoints will include rates of asymptomatic  
343 hypoglycemia or nocturnal hypoglycemia as detected by CGM, which will typically  
344 not be detected by the standard-of-care SMBG.

345

346 Table 1- Schedule of events during the study period

Visit # (V) Phone visit (P)	V1*	V2*	P3*	P4*	P5*	V6*	P7*	P8*	P9*	V10**	P11**	V12**	V13**	P14**	V15**	P16**	V17**	V18**
Time-wks	-2	0	1	2	3	4	5	6	7	8	10	12	14	16	20	24	26	27
Inf. Consent		X																
Inc/exclusion	X	X																
Rando@		X																
Withdrawal cx		X	X	X	X	X	X	X	X	X	X	X	X	x	X	x	x	
Drug compl		X				X				X		X	X	x		X	x	
Dose adjust			X	X	X	X	X	X	X	X	X	X	X	x	X	X	x	
Efficacy																		
Vital signs@	X	X				X				X		X	x		x	X	x	
Phys exam	x																	
Pregnancy test*	X	X				X				X		X					X	
Body Measurements	X	X				X				X		X	X		x		X	
BMI	X	X				X				X		X	x		x			
HbA1c	x											X					X	
CMP	X&											X					X	
Fasting glucose&		X				X				X		X				X	x	
Instruct 8-p SMBG	x				X						X					X		
Collect 8-pt SMBG		X				X						X					X	
Labs	X^																X^*	
7d-CGM insert	X 											X					X	
7d- CGM collect	x											x					x	
DTSQ&TRIM-D		X										X					X	
Safety																		
Adverse events			X	X	X	X	X	X	X	X	X	X	x	X	X	X	X	
Hypoglycemia			X	X	X	X	X	X	X	X	X	X	x	X	X	X	X	
Trial material																		
Drug dispensing		X				X				X		X						
Drug account			X		X					X		X				x		
End-of-Trial															x			

391 \*+/- 3 days. \*\*+/- 7 days. Labs: ^ pregnancy test, ketones, lipid panel^\* and GAD65 (If concern for Type 1 diabetes, GAD65 and ketones  
392 will be ordered during screening, per PI discretion). Pregnancy test for WOCP as deemed by investigator & fasting defined as at least 8  
393 hours without food or drinks or diabetes medications, except water and other prescribed medications.  +/- 7 days, but before  
394 randomization visit. Fasting glucose could be obtained from a chemistry sample obtained during the visit or POC BG. Body  
395 measurement includes: weight, height and waist and hip circumference. @ During "randomization" and "vital signs" visits, subjects will  
396 receive training on device use.

397 **Treatment of subjects:**

398 **Group 1) IDegLira Group**

399 • Discontinue OADs (SU, DPPIVi, glinides, and pioglitazone), except metformin  
400 (unless contraindicated) and SGLT2i.

401 • Start IDegLira at 16 dose steps (degludec 16 units/liraglutide 0.6 mg), per U.S  
402 labeling indications and/or provider discretion.

403 • IDegLira will be given once daily, at the same time of the day with or without food.

404 • IDegLira will be titrated until the maximum dose (50 steps) is reached, up to target fasting  
405 BG between 70 and 100 mg/dl (Treat-To-Target Trial protocol), see algorithm below.

406 • Titration will occur twice a week: 1) self-titration by patients once a week and 2) phone call/  
407 contact by research team once a week, for the initial 8 weeks. After that, patients will self-  
408 titrate study medications per dosing algorithm.

409 • IDegLira will be titrated by 2-step-dose increment (2 IU of degludec and 0.072 of liraglutide),  
410 to a maximum of 8 steps per week.

411 • The maximum allowed dose of IDegLira 50 dose steps provide 50 U of degludec and 1.8mg  
412 of liraglutide.

413 • Titration will be performed twice weekly (every 3 to 4 days) based on the previous self-  
414 monitored fasting (pre-breakfast) BG measurement (mean of 3 consecutive days). Patients  
415 will be provided with self-titration algorithms for insulin adjustments.

416 • Subjects not at goal (fasting or mean SMBG from 3 consecutive days > 300 mg/dl) requiring  
417 > 50 dose steps of IDegLira, will be considered “treatment failures”. Degludec will be added  
418 to IDegLira as “rescue” basal insulin therapy. The dose of IDegLira will remain unchanged.

419 • The dose of “rescue” Degludec will be recorded and titrated twice weekly to target FPG of  
420 70-100 mg/dl, per provider discretion, as shown below.

Titration algorithm for IDegLira and Degludec pens	Insulin dosage IU/d)*
$\geq 181$	8
141-180	6
121-140	4
101-120	2
71-100	no adjustments
$<70$	-2 If dose $> 45$ U/d, decrease by 10%
$<56$	-4 If dose $> 45$ U/d, decrease by 10%

\* Maximum titration dose per week: 8 units

